Appendix D Investigator asthma knowledge questionnaire

CAREFORALL Asthma Knowledge Test

Your Name:

Where the hospital is located: province (autonomous region) __, city __

Hospital Tier level: Tier 3 __ Tier 2 __

Doctor Title: Chief Physician __ Deputy Chief Physician __ Attending Physician __ Resident Physician __

Part 1 Single Choice Questions

1. Asthma is an __ inflammatory disease of the airways ()

- A. acute
- B. chronic

2. Cough variant asthma is __ as the sole or main symptom ()

- A. cough

- B. Breathing

- C. Shortness of breath

3. Mild asthma: those who can achieve complete control after the first treatment ()

- A. step1

- B. step 2

- C. step1,2

4. Risk factors for future exacerbations of asthma include: uncontrolled asthma, continuous exposure to allergens, comorbidities, irregular medication, poor compliance, and visits to the emergency room or hospitalization for acute asthma exacerbations in the past year. ()

- A. Ture

- B. False

5. Can FENO be used to predict and assess the response to ICS therapy? ()

- A. Flase

B. Ture

6. During an acute asthma attack, the preferred reliever drug is ()

A. Salbutamol Aerosol

B. Low-dose ICS + formoterol

C. ICS

7. The most effective drug for controlling asthmatic airway inflammation is ()

A. Leukotriene Modulators

B. Glucocorticoids

C. Aminophylline

8. If asthma control is maintained for at least _ months, step down treatment can be considered to find the lowest effective treatment step for maintaining asthma control ()

A. 14 days B. 1 month C. 3 months D. 6 months

9. In step 1, if patients only presented occasional, transient daytime symptoms less than twice a month, each last several hours, without nocturnal symptoms and risk of acute exacerbation, meanwhile normal lung function. The recommended treatment is ()

A. As-needed low-dose ICS + formoterol inhalation

B. Inhaled low-dose ICS and as-needed inhaled SABA

C. Inhaled anticholinergic drugs (e.g, ipratropium bromide), oral SABA, or short-acting theophylline

10. In step 2, recommended treatment is ():

A. LTRA

B. Low-dose ICS plus as-needed reliever medication

11. Patients with persistent asthma symptoms or acute exacerbations who are treated at Step 4 need to be referred to an asthma specialist for treatment of severe asthma. Do inhalation technique and adherence need to be assessed before considering severe asthma? ()

A. required

B. not required

12. The frequency of follow-up for asthma treatment depends on the level of initial treatment, responsiveness to treatment, and the patient's ability to self-manage. Follow-up visits are usually required every _ weeks after initiation of treatment. ()

A.2-4

B.8

C.12

13. Does step down treatment can completely discontinue ICS without increasing the risk of exacerbations ().

A. True

B. False

14. For CVA, patients with chronic cough who cannot perform bronchial provocation test clinically and have no features suggesting other causes of chronic cough can be considered for empirical treatment according to CVA, but further examination is required when the treatment is ineffective. ()

A. False

B. Ture

15. Poor symptom control of severe asthma, meet criteria when ()

A. ACT≥19, ACQ greater than 1.5

B. ACT≤19, ACQ less than 1.5

C. ACT≤19, ACQ greater than 1.5

D. ACT≥19, ACQ less than 1.5

16. The China Pulmonary Health Survey (CPH) study showed that the prevalence of asthma in the Chinese population aged 20 years and above using the asthma questionnaire ()

A.1.2%

B.4.2%

C.8.2%

D 10.2%

17. For asthma during pregnancy, should ICS be reduced or discontinued based on safety considerations? ()

A. Yes

B. No

Part II Multiple Choice Questions

18. Objective tests for variable airflow limitation in asthma include ()

A. After inhalation of bronchodilators, FEV1 increased by >12%, and the absolute value of FEV1 increased by >200 ml)

B. FEV1 increased by >12% compared with the baseline value after 4 weeks of anti-inflammatory treatment, and the absolute value of FEV1 increased by >200 ml (excluding respiratory tract infection).

C. Positive bronchial challenge test

D. Average daily diurnal variability or PEF weekly variability of peak expiratory flow

19. Asthma Treatment Goals ()

A. To achieve good control of asthma symptoms and maintain normal activity levels

B. Minimize exacerbations and deaths

C. Minimize irreversible damage to lung function

D. Minimize the risk of drug-related adverse reactions

20. How many ways are there to step up the treatment of asthma? ()

A. Escalation of maintenance therapy

B. Short-course booster therapy

C. Daily adjustment of treatment

21. Severe asthma includes: ()

- A. Step 4 treatment maintains control, but step-down treatment will lose control
- B. Step 4 treatment fails to maintain control and requires step 5 treatment
- C. Uncontrolled asthma even with the above treatments

22. Severe asthma treatment drugs include ()

- A. ICS and OCS, LABA, LTRA, LAMA,
- B. Sustained release theophylline
- C. Macrolide drugs
- D. Biological drugs

23. What do you think the diagnosis of asthma is based on ()

- A. Recurrent episodes of wheezing and shortness of breath, with or without chest tightness or cough, occur frequently at night and in the morning, and are often related to exposure to allergens, cold air, physical and chemical stimuli, upper respiratory tract infections, exercise, etc.
- B. Chronic persistent asthma that is uncontrolled at the time of attack and partly, with scattered or diffuse wheezing in both lungs, prolonged expiratory phase
- C. Can be relieved by treatment or spontaneously relieved
- D. Have any of the objective tests for airflow limitation
- E. Excluding wheezing symptoms caused by other diseases

24. Assessment of asthma symptom control, including assessing whether the patient has () in the past 4 weeks:

- A. Daytime Asthma Symptoms
- B. Waking up at night due to asthma
- C. Use reliever medication
- D. Activity limitation due to asthma

25. You think the CTVA diagnosis is based on: ()

- A. Chest tightness as the only or main symptom, without wheezing, shortness of breath and other symptoms and signs of typical asthma
- B. Possesses any of the objective tests for variable airflow limitation
- C. Excluding chest tightness caused by other diseases
- D. Anti-asthma treatment is effective

Appendix E Inhaler skill score assessment checklist

Inhaler skill score assessment checklist

MDI (Ventolin, Ipratropium Bromide Solution for Inhalation ,Beclomethasone Dipropionate and Formoterol Inhalation Aerosol , Glycopyrronium Bromide and Formoterol Fumarate Inhalation Aerosol) Steps			
Prepare	1	Clean your mouth, sit upright and tilt your head back slightly to keep your airway open. Open the nozzle dust cap	①True ②False
start up	2	Shake vigorously to suspend the liquid evenly	① True ②False
exhale	3	Exhale as fully as possible	①True ②False
Bite	4	Lips closed to hold the mouthpiece	①True ②False
Inhale	5	While inhaling slowly and deeply, press on the bottom of the canister and continue to inhale	①True ②False
hold breath	6	Move the mouthpiece away from your lips, hold breath for as long as possible for 6 to 10 seconds and then exhale slowly	①True ②False
repeat or finish	7	Cover the protective cap, gargle with ICS medicines	① True ②False
DPI (HandiHaler) Steps			
Prepare	1	Clean your mouth, sit upright and tilt your head back slightly to keep your airway open. Open dust cap and nozzle	①True ②False
start up	2	Place the capsule in the central chamber, close the mouthpiece until you hear a click, keep the inhaler upright, press the pierce button all the way down, and release	① True ②False
exhale	3	Exhale as fully as possible and stay away from the mouth	①True ②False

Bite	4	Lips closed to hold the mouthpiece	①True ②False
Inhale	5	Take a quick, deep breath to rotate the capsule until no more air is drawn in	①True ②False
hold breath	6	Move the mouthpiece away from your lips, hold your breath for as long as possible for 6 to 10 seconds and then exhale slowly	①True ②False
repeat or finish	7	Pour out the used capsule after inhalation, close the mouthpiece and dust cap	① True ②False
DPI (Turbuhaler) Steps			
Prepare	1	Clean your mouth, sit upright and tilt your head back slightly to keep your airway open. Unscrew and pull out the cap	①True ②False
start up	2	Take the straight device, hold the red handle part and the middle part of the dowel, rotate it to the end in one direction, and then rotate it to the end in the opposite direction, you will hear a clicking sound during this process	①True ②False
exhale	3	Exhale as fully as possible and stay away from the mouth	①True ②False
Bite	4	Hold the unit horizontally, with lips that wrap around the nozzle without blocking the vents	①True ②False
Inhale	5	Inhale quickly and forcefully until no more air is drawn in	①True ②False
hold breath	6	Move the mouthpiece away from your lips, hold your breath for as long as possible for 6 to 10 seconds and then exhale slowly	①True ②False
repeat or finish	7	Move the mouthpiece away from your lips, hold your breath for as long as possible for 6 to 10 seconds and then exhale slowly	① True ②False

DPI (Diskus) Steps			
Prepare	1	Clean your mouth, sit upright and tilt your head back slightly to keep your airway open.	①True ②False
start up	2	Open dust cap and nozzle	①True ②False
exhale	3	Place the capsule in the central chamber, close the mouthpiece until you hear a click, keep the inhaler upright, press the pierce button all the way down, and release	①True ②False
Bite	4	Exhale as fully as possible and stay away from the mouth	①True ②False
Inhale	5	Lips closed to hold the mouthpiece	①True ②False
hold breath	6	Take a quick, deep breath to rotate the capsule until no more air is drawn in	①True ②False
repeat or finish	7	Cover the protective cap, gargle with ICS medicines	② True ②False
DPI (®Ellipta) Steps			
Prepare	1	Clean your mouth, sit upright and tilt your head back slightly to keep your airway open	① True ②False
start up	2	Open the dust cap until you hear a click	①True ②False
exhale	3	Exhale as fully as possible and stay away from the mouth	①True ②False
Bite	4	Hold the device horizontally, lips wrapping the nozzle	①True ②False
Inhale	5	Inhale quickly and forcefully until no more air is drawn in	①True ②False
hold breath	6	Move the mouthpiece away from your lips, hold your breath for as long as possible for 6 to 10 seconds and then exhale slowly	①True ②False

repeat or finish	7	Turn off device	① True ②False
DPI (Indacaterol Maleate and Glycopyrronium Bromide Powder for Inhalation, Hard Capsules) Steps			
Prepare	1	Clean your mouth, sit upright and tilt your head back slightly to keep your airway open. Open dust cap and nozzle	①True ②False
start up	2	Take one capsule out of the package, put it in the central compartment, close the nozzle until you hear a click, press the piercing buttons on both sides firmly, press the piercing buttons all the way, and release	True ②False
exhale	3	Exhale as fully as possible and stay away from the mouth	①True ②False
Bite	4	lip wrap nozzle	①True ②False
Inhale	5	Take a quick, deep breath to rotate the capsule until no more air is drawn in	①True ②False
hold breath	6	Move the mouthpiece away from your lips, hold your breath for as long as possible for 6 to 10 seconds and then exhale slowly	①True ②False
repeat or finish	7	Pour out the used capsule after inhalation, close the mouthpiece and dust cap	①True ②False
SMI (Tiotropium Bromide Inhalation Spray) Steps			
Prepare	1	Clean your mouth, sit upright, tilt your head slightly back to keep the airway open, close the protective cover, turn the transparent base half a turn in the direction indicated by the arrow on the label until you hear a click, and fully open the dust cap	①True ②False
start up	2	Exhale as fully as possible	①True ②False
exhale	3	Lips wrap the mouthpiece, do not cover the vents	①True ②False

Bite	4	Point the device at the back of the throat and press the dosing button	①True ②False
Inhale	5	Inhale slowly and deeply for as long as possible until no more air is inhaling	①True ②False
hold breath	6	Move the mouthpiece away from your lips, hold your breath for as long as possible for 6 to 10 seconds and then exhale slowly	①True ②False
repeat or finish	7	Close the dust cap, suck again (2 clicks = 1 dose), repeat the steps	① True ②False

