8.1.8 Inhaler skill score assessment

Regarding the technical standards of inhalation, there are relevant regulations in national guidelines, and the overall process is consistent ([Chinese expert consensus on standard application of inhalation device in stable chronic airway disease patients, 2019](#)). Regarding the technical standards of inhalation, there are relevant regulations in national guidelines, and

the overall process is consistent (Chinese expert consensus on standard application of inhalation device in stable chronic airway disease patients, 2019). The study is designed for 7 steps, with 1 point for each step, and the full score is 7 points. The technical evaluation of inhaler is based on devices which commonly used by researchers participating in the study. Inhaler skill shall be assessed by the group from leading site before and after education, and the subjects shall be instructed only after investigators pass this assessment. Random inspections will be conducted during the follow-up period. V1 allows the subjects to demonstrate the inhalation process such as the dosing or the using method with the prepared device, and the researcher controls the operating standard as the baseline. It is recommended that each centre recommend 1-2 physicians or nurses, who are trained and qualified to be responsible for this work, and adopt uniform standards. (Appendix E)

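### In Appendix E the breath-hold is missing from the Diskus form and printed twice on the Turbuhaler form, so inhaler skill totals scored as printed can be wrong for those two devices

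*Protocol*

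**What the plan says.** Protocol section 8.1.8 sets the scoring rule: "The study is designed for 7 steps, with 1 point for each step, and the full score is 7 points". Appendix E prints one seven-row form for each of seven devices. Every form has the same row labels (*Prepare, start up, exhale, Bite, Inhale, hold breath, repeat or finish*), then a sentence describing the action and a True/False cell.

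- **Diskus.** Row 3, labelled *exhale*, begins "Place the capsule in the central chamber, close the mouthpiece until you hear a click, keep the inhaler upright". Row 6, labelled *hold breath*, reads "Take a quick, deep breath to rotate the capsule until no more air is drawn in". Both sentences also stand on the HandiHaler form, in rows 2 and 5.
- **Turbuhaler.** Rows 6 and 7 carry the same sentence: "Move the mouthpiece away from your lips, hold your breath for as long as possible for 6 to 10 seconds and then exhale slowly". Row 7 is labelled *repeat or finish*.
- **For comparison.** The other six forms all end with a closing step; on Ellipta it is "Turn off device".
- **SMI.** The sentence "Point the device at the back of the throat and press the dosing button" stands under *Bite*. Rows 2 to 4 are one label out.

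The Schedule of Activities collects the patient score at V1, V2, V3 and V5. Section 8.1.8 treats V1 as its baseline, and SAP section 5 lists the score as item 17 of the second interim analysis.

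**The concern.** The score is a plain count of rows marked True. If a row describes an action that does not belong to the device, or repeats another row, the count no longer measures the seven intended actions with equal weight. On five forms the breath-hold is worth one point. As printed, it is worth nothing on Diskus and two points on Turbuhaler, where closing the device is worth nothing. Two Diskus rows also leave the assessor to decide how to mark a capsule action.

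What is at stake is the validity of the skill totals, and of their change from V1, for patients assessed on these two devices. Inhaler technique is also one of the program's own performance checkpoints (protocol section 6.1.2.3), so sites have reason to rely on this form.

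**Working it through.** **1. The plan's own figure.** Each form has 7 rows at 1 point, so 7 × 1 = 7, which agrees with section 8.1.8. Seven forms give 7 × 7 = 49 rows.

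**2. Diskus rows compared with the other forms (sentences paraphrased).**

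| Row | Label | Action in the Diskus sentence | Same sentence also at |
|---|---|---|---|
| 1 | Prepare | mouth and posture | HandiHaler row 1, first part |
| 2 | start up | open cap and nozzle | HandiHaler row 1, last part |
| 3 | exhale | load and pierce a capsule | HandiHaler row 2 |
| 4 | Bite | exhale | HandiHaler row 3 |
| 5 | Inhale | lip seal | HandiHaler row 4 |
| 6 | hold breath | inhale so that the capsule rotates | HandiHaler row 5 |
| 7 | repeat or finish | replace cap, gargle | MDI row 7 |

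HandiHaler row 1 has been split in two. This pushes the rest down one row and leaves no room for HandiHaler row 6, the breath-hold.

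**3. Rows per form, by the printed sentence.**

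| | MDI | HandiHaler | Turbuhaler | Diskus | Ellipta | Hard capsules | SMI |
|---|---|---|---|---|---|---|---|
| Breath-hold | 1 | 1 | 2 | 0 | 1 | 1 | 1 |
| Closing step | 1 | 1 | 0 | 1 | 1 | 1 | 1 |

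**4. Totals.** Printed total = 7 − (rows describing the missed action) − c. Here c is the number of Diskus capsule rows (3 and 6) marked False: c = 2 on a strict reading, 1 if a quick deep breath is accepted for row 6, and 0 if both are marked True despite the wording. On Turbuhaler c = 0. The assumption is that a Diskus takes no capsule. The documents do not say so, but both capsule forms end by emptying a used capsule and the Diskus form does not.

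| Performance | Corrected form | Turbuhaler as printed | Diskus as printed |
|---|---|---|---|
| No fault | 7 | 7 | 7 − c = 7, 6 or 5 |
| Only breath-hold missed | 7 − 1 = 6 | 7 − 2 = 5 | 7 − 0 − c = 7, 6 or 5 |
| Only closing step missed | 7 − 1 = 6 | 7 − 0 = 7 | 7 − 1 − c = 6, 5 or 4 |

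The first two Diskus lines are identical, so the total carries no information on the breath-hold.

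**5. All pass/fail patterns.** Seven actions, each done or missed, give 2^7 = 128 patterns. Turbuhaler totals are off by 1 point, in either direction, whenever breath-hold and closing step differ: 128 × 1/2 = 64 patterns. For Diskus, row 3 is taken as never met and opening the device as the start-up action. Totals are then low by 1 in 64 patterns (row 6 read leniently), or by 1 or 2 in 128 × 3/4 = 96 patterns (row 6 read strictly). These are counts of patterns, not of patients.

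**6. Change score.** Take a patient who misses only the breath-hold at V1 and makes no error at V5 on the same device. The change is 7 − 6 = +1 on a correct form and 7 − 5 = +2 on Turbuhaler. On Diskus it is 0, if the capsule rows are marked the same way at both visits.

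**7. Rows that matter.** Diskus 3 and 6 and Turbuhaler 7 can change a total: 3/49 = 6.1%. Diskus rows 4 and 5 and SMI rows 2 to 4 each describe a proper action exactly once, under the wrong label, so a total scored by the sentence is unaffected.

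**The case against.** The strongest reply is that this is a copying slip in an appendix and that trained assessors would not follow it literally. Section 8.1.8 does have safeguards: "Inhaler skill shall be assessed by the group from leading site before and after education", random inspections, a recommendation of one or two trained assessors per centre working to uniform standards, and a reference to national guidelines and an expert consensus as the technique standard. These make literal scoring less likely. They do not correct the form or say that it may be overruled, and the content of the consensus cannot be judged from these documents.

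Three further limits stand in part or in full:

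- The CRF (version 5.0 per SAP section 1) and the exploratory endpoint sections cannot be seen. Either could hold corrected rows or a scoring note.
- A constant form error cancels in part from a within-patient change. That is true of the capsule rows if they are marked consistently, but not of the breath-hold (step 6).
- An extraction fault is unlikely for Diskus, where another device's text runs in order through numbered rows, each with its own True/False cell. It is less firmly excluded for the single Turbuhaler row.

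A reader might also infer more than the documents support:

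- **Label against sentence.** One could count every row where label and sentence disagree (Diskus 4, SMI 3, Turbuhaler 1, so 8 of 49) and argue that assessors would split between the two. But the True/False cell closes a described action, and a label such as *Bite* can hardly be scored alone. Five of those eight rows leave the total unchanged when the sentence is scored.
- **Gatekeeping.** Section 8.1.8 says that "the subjects shall be instructed only after investigators pass this assessment". It gives no pass mark and the leading-site group makes the assessment, so no wrong pass or fail can be derived.
- **Distorted study results.** The device mix is not given and no visible text plans a comparison across devices.

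**Conclusion.** The point holds: the form is wrong as written, with minor severity. If rows are scored by their printed sentence, a single breath-hold or closing-step fault shifts a Turbuhaler total by 1 point, down or up. A Diskus total is blind to the breath-hold and depends by up to 2 points on how the capsule rows are marked. Three of 49 rows are responsible.

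This rests on the printed sentence being the scored item, on a Diskus having no capsule, and on the CRF page repeating Appendix E, none of which the documents settle. The effect stays within the inhaler skill score. The primary endpoint, the secondary endpoints and the power calculation do not use it.

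**What to change.** - Rewrite Diskus rows 2 to 6 as device loading, exhale, lip seal, inhale and breath-hold, taking the loading wording from the technique standard cited in section 8.1.8.
- Replace Turbuhaler row 7 with a closing step.
- Realign the SMI labels in rows 2 to 4.
- Check the CRF page against the corrected form and reissue the form to sites.
- For data already collected, ask sites how the affected rows were scored. Report the score by device and state the limitation.

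I would not add a sensitivity analysis on a reduced set of items. Leaving out Diskus rows 3 to 6 keeps only 7 − 4 = 3 rows (posture, opening, closing), with no inhalation step, and no analysis can recover a breath-hold that was never scored.

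The cost is one appendix page, the CRF page if it is affected, one query to about 30 sites, and one or two sentences in the SAP. If all V5 assessments are complete, only the site query and the reporting sentences still matter for the data.

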Appendix F Abbreviations

Abbreviation or special term	Explanation
AE	Adverse Event
BPT	Bronchial Provocation Test
CRO	Contract Research Organisation
CSP	Clinical Study Protocol
CSR	Clinical Study Report
eCRF	electronic Case Report Form
FeNO	Fractional exhaled nitric oxide
GCP	Good Clinical Practice
ICF	informed consent form
ICH	International Council for Harmonisation
IEC	Independent Ethics Committee
IMP	Investigational Medicinal Product
IRB	Institutional Review Board
KPI	Key Performance Indicator
MCID	Minimum clinical important difference
MARS-A	Medication Adherence Report Scale for Asthma
PEF	Peak expiratory flow
PFT	Pulmonary Function Testing
PHL	Potential Hy's Law
PI	Principal investigator
QIP	Quality Improvement Program
SAE	Serious adverse event
SAP	Statistical analysis plan
SoA	Schedule of Activities

List abbreviations and definitions of specialized or unusual terms, measurements, or units. Examples are provided below. These can be modified at study level.

Abbreviation or Specialized Term	Definition
AE	Adverse Event
BPT	Bronchial Provocation Test
CRO	Contract Research Organisation
CSP	Clinical Study Protocol
CSR	Clinical Study Report
eCRF	electronic Case Report Form
FeNO	Fractional exhaled Nitric Oxide
GCP	Good Clinical Practice
ICF	Informed Consent Form
ICH	International Council for Harmonisation
IEC	Independent Ethics Committee
IMP	Investigational Medicinal Product
IRB	Institutional Review Board
KPI	Key Performance Indicator
MCID	Minimum Clinical Important Difference
PEF	Peak Expiratory Flow
PFT	Pulmonary Function Testing
PHL	Potential Hy's Law
PI	Principal Investigator
QIP	Quality Improvement Program
SAE	Serious adverse event
SAP	Statistical Analysis Plan
SoA	Schedule of Activities

AMENDMENT HISTORY

CATEGORY Change refers to:	Date	Description of change	In line with CSP?	Rationale
N/A	10/21/2022	Initial approved SAP	Yes	N/A
N/A	7/4/2022	Add 2 interim analysis per Protocol v2.0	Yes	N/A
Exploratory Endpoints	7/4/2023	Add below exploratory endpoints per Protocol v2.0- ● ● ● ● ● ●	Yes	N/A

CATEGORY Change refers to:	Date	Description of change	In line with CSP?	Rationale
		characteristic and asthma control level		
N/A	2/18/2024	Add the baseline and analysis window for investigator analysis. Add scope of the interim analysis.	Yes	N/A
Exploratory Endpoints	2/18/2024	Add below exploratory endpoints per protocol V3.0 ●	Yes	N/A
NA	8/19/2024	Specify the visit windowing strategy for investigators in details, similar to subject's windows rule.	Yes	N/A
Subgroup Anlyses	8/19/2024	Move all subgroup analyses to a separate section 4.2.4. Specify the definition and cut-off threshold for subgroups.	Yes	N/A
Exploratory Endpoints - 3	8/19/2024		Yes	N/A
Exploratory Endpoints -5	8/19/2024		No	Prior and concomitant medication page does not collect the investigator ID number, so deleted.
NA	8/19/2024	Change wording “ partially controlled” to “ partly controlled” for ACQ-5 (0.75 to 1.5).	No	Based on comments from expert opinion, the word “partially” is

CATEGORY Change refers to:	Date	Description of change	In line with CSP?	Rationale
				not correct for ACQ-5 (0.75 to 1.5), so changed to “partly”.
Safety analyses	8/19/2024	Deleted safety analysis part to be consistent with CSP V3.0 (with no safety objective or endpoints in CSP)	Yes	N/A

